Any serious unexpected adverse events (grade 4 toxicity per Common Terminology Criteria for Adverse Events version 3.0) will lead to suspension of study enrollment for determination of attribution of the event to study procedure. The principal investigator will review and evaluate these events in relation to the study procedures and outcomes before further patients are enrolled. Any fever occurring within twelve hours of the stem cell infusion requiring hospital admission will be considered an expected serious adverse event. This event will require prompt reporting to the Institutional Review Board (IRB), but will not require suspension of the study. In the event of documented graft versus host disease, grade II or above at any site, the study will be suspended to assess and evaluate the situation and to reconsider study procedures. The IRB may determine that the study should be terminated based on their review of reported SAEs.

9. Facilities Utilized In the Study

The stem cell infusion will be performed at Children's Hospital of Cincinnati Medical Center.

V. POTENTIAL BENEFITS

There may be no benefit from participating in this study. However, the information learned from this study may help make better the health care that is given to patients with primary immunodeficiency disorders in the future.

This CD34+ stem cell infusion procedure may be able to increase donor chimerism, resulting in correction of immunodeficiency, thrombocytopenia or enzyme deficiency sufficient to reverse present disease or clinical condition. If this happens, the patient will no longer require transfusions of platelets and have less risk of infection. This procedure may also be able to decrease the risk of malignant transformations that potentially occur in some of untreated primary immunodeficiencies. These outcomes would be a benefit to participants.

VI. POTENTIAL RISKS, DISCOMFORTS, INCONVENIENCES AND PRECAUTIONS

1. Known or potential risks, discomforts, or inconveniences

Infusion reactions: Infusion reactions are unlikely because of the highly purified nature of the product. However there is a potential risk of reaction including fever, chills, anaphylaxis, rash, shortness of breath. Transfusions also carry the risk of hepatitis, human immunodeficiency virus and viral pneumonia due to cytomegalovirus.

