Graft versus host disease (GVHD): GVHD is unlikely as a low number of T-cells will remain after cell selection and the recipients already have stable mixed chimerism with cells from their donors. Acute GVHD can cause a skin rash, liver dysfunction, and/or enteritis, and is potentially fatal. Chronic GVHD is a multi-organ autoimmune disease, which may resolve over several months or years or lead to death, commonly from infection.

2. Precautions that will be taken to monitor and avoid the above mentioned risks, discomforts, and inconveniences, including methods for detecting adverse events

Infusion reactions: The risk of transfusion reaction will be minimized by appropriate testing of the donor and products, and by use of pre-medication. Pre-medications will be given according to standard practice. Patients will be monitored according to CCHMC guidelines during stem cell infusion for any infusion reactions. To reduce the risk of product infusion, CD34+ stem cells will be highly T-cell depleted. Should an infusion reaction occur it will be treated with supportive therapy according to standard transplant procedure.

Graft versus host disease: The risk of developing a new case of GVHD is anticipated to be very low. No GVHD prophylaxis will be given. Any occurring

GVHD would be treated according to accepted standards.

3. The method of monitoring study conduct.

All grade 3 or greater adverse events occurring during this study will be recorded on the case report forms. The principal investigator will review each event and assess its relationship to study events as to whether the event is unrelated, unlikely related, possibly related, probably related, or definitely related to the study device. The CTCAE Version 3.0 will be used to evaluate these adverse events.

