This population of patients, by nature of their various disease/conditions and due to effects from the original allogeneic hematopoietic stem cell transplantation (with a full preparative regimen), often continue to experience disease and therapy-related complications and are frequently hospitalized for observation and/or treatment of these conditions. As these patients do not receive any preparative therapy as participants in this study, the risk of study-related toxicity is expected to be minimal. Consequently any serious adverse events, as defined by the IRB guidelines, that are determined to be possibly, probably or definitely related to the study device will be reported according to IRB reporting regulations. However, serious adverse events determined to be related to the patient's underlying disease/condition or to the first transplant procedure, including hospitalizations or prolongation of hospitalizations resulting from such events, will not require expedited reporting to the IRB. These events will be reported annually with the progress report. Please note that for the purpose of this study we will exclude the report of hematologic toxicities, as these subjects, by virtue of their underlying disease and/or condition may present with baseline hematologic toxicity.

Although these subjects will be followed on study for up to 3 years post infusion, all adverse events (as described above) will be captured for the first 30 days post stem cell infusion. Thereafter, only related adverse events will be recorded on case report forms.

4. Methods for maintaining data quality and confidentiality

Data quality is monitored and audited by the Center for International Blood and Marrow Transplant Research and the National Marrow Donor Program. Confidentiality is maintained as per section VI.

5. An assessment of accrual (timely enrollment) and the handling of dropouts.

Accrual assessment will be evaluated by the principal investigator with the annual progress review. Subjects who do not complete a full six months of follow up will not be counted in the total stratum accrual and will be replaced.

6. Risk assessment recommendation

- Minimal risk but with direct benefit to participants
- Minimal risk but without direct benefit to participants

More than minimal risk but with direct benefit to participants

More than minimal risk but without direct benefit to participant

7. Data and Safety Monitoring Plan

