This study does not require a DSMB or medical monitor because the patient is already a mixed chimera (has both donor and own cells) and likely tolerant of donor cells. In addition, the patient will not receive any preparative therapy prior to stem cell infuse, thus decreasing the risk of toxicities by the patient. Therefore, the principal investigator will be responsible for monitoring the study.

The data generated during this trial will be monitored by the Principal Investigator for safety and compliance with protocol-specified requirements. The Principal Investigator will review all protocol related lab results for each patient enrolled on the protocol, and each patient will be examined by the Principal Investigator or the physician following the patient during their required follow-up visits. All planned testing is medically indicated for patients undergoing treatment regardless of their participation in this research study. The study PI and research coordinator will review the study progress regularly. Patients entered on the trial and adverse events will be reviewed to ensure that the study is implemented as outlined in the protocol.

All decisions regarding study continuation, modification, or termination will be reported immediately or annually, as appropriate, to the IRB, FDA, and other appropriate agencies. Reports for events determined by the investigator to be possible or definitely related to study participation and reports of events resulting in death should be forwarded in compliance with current IRB policy and applicable federal regulations.

Any serious unexpected adverse events (grade 4 toxicity per Common Terminology Criteria for Adverse Events version 3.0) which occur during the stem cell infusion or within thirty days after the infusion will be expeditedly reported to and evaluated by the Principal Investigator, as well as the IRB (see section VI-3). Thereafter, only events related to the study procedures will be captured on case report forms for each subject on study.

VII. CONFIDENTIALITY

Every effort will be made to maintain patient confidentiality. Absolute confidentiality cannot be guaranteed. Patient information may be disclosed if required by law. The FDA, Hoxworth Blood Center and the Cincinnati Children's Hospital Medical Center Institutional Review Board will have access to the records.

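### The enrolment-suspension rule names grade 4 without a floor, does not name death, states no time window, and does not fit the 30-day event-capture rule

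*Combined protocol and SAP*

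**What the plan says.** Four rules, in three places of the combined protocol and SAP, bear on this point.

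- **Suspension (section 7, Stopping Rules).** "Any serious unexpected adverse events (grade 4 toxicity per Common Terminology Criteria for Adverse Events version 3.0) will lead to suspension of study enrollment". The stated purpose of the pause is "for determination of attribution of the event to study procedure". No time limit is given. A second trigger follows in the same paragraph: "In the event of documented graft versus host disease, grade II or above at any site, the study will be suspended". The paragraph ends with a discretionary power: "The IRB may determine that the study should be terminated based on their review of reported SAEs".
- **Recording (section VI.3, method of monitoring study conduct).** "All grade 3 or greater adverse events occurring during this study will be recorded on the case report forms". Later in the same section, patients are "followed on study for up to 3 years post infusion", but full capture is confined to the first 30 days. Then: "Thereafter, only related adverse events will be recorded on case report forms".
- **Expedited reporting (section VI.7, Data and Safety Monitoring Plan).** The same class of event, again described as grade 4, is covered for events "which occur during the stem cell infusion or within thirty days after the infusion will be expeditedly reported" to the principal investigator and the IRB. After that, only events related to study procedures go on the case report forms.
- **Deaths (section VI.7).** Reports of events resulting in death are to be forwarded under IRB policy and federal regulations. No suspension is attached to them.

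Section VI.7 also states that the trial needs no DSMB or medical monitor and that the principal investigator monitors it.

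**The concern.** A rule that halts enrolment should cover the worst outcome without the reader having to infer it. Here the grade is a single value. The same authors write a floor when recording events and when setting the GVHD trigger, so the missing floor is conspicuous. Death is treated as a separate category, and only as a reporting duty.

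The second difficulty is the order of steps. The Stopping Rules pause enrolment first and settle relatedness during the pause. After day 30 the recording rule requires relatedness to be judged before the event reaches a case report form. The judgement that the pause is meant to inform then decides whether the event is recorded at all.

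Patient protection is at stake. Apart from GVHD, this is the only toxicity-based trigger in the plan, and no independent body is in place to apply it in spirit where the wording falls short.

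**Working it through.** The rule has no numerical threshold or error rate, so the check is a comparison of the texts.

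**Step 1. The rules side by side.**

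| Rule | Severity named | Death named? | Window | Relatedness decided |
|---|---|---|---|---|
| Suspension, Stopping Rules | Grade 4, no floor | No | None stated | During the suspension |
| Suspension for GVHD, Stopping Rules | Grade II and upward | Not needed | None stated | Not a condition |
| Expedited report, VI.7 | Grade 4, no floor | No | Infusion to day 30 | Not a condition up to day 30 |
| Death reports, VI.7 | Not applicable | Yes | None stated | Not a condition |
| Recording, VI.3 opening sentence | Grade 3 and upward | No | During the study | Not a condition |
| Recording, VI.3 later sentences | As above | No | All to day 30, then related only | Before recording, after day 30 |

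**Step 2. Cases run through the printed text.**

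1. *Unexpected grade 4 event by day 30.* Enrolment is suspended, the event is reported in expedited fashion, and it is recorded. On timing, the rules agree.
2. *Unexpected death by day 30, no GVHD of grade II or above.* It is reportable as a death. Read literally, neither suspension trigger is met.
3. *Death with documented GVHD of grade II or above.* The second trigger suspends the study.
4. *Unexpected grade 4 event after day 30, judged related.* The suspension rule applies and the event is recorded. The rule can operate.
5. *Unexpected grade 4 event after day 30, not judged related.* The suspension rule still calls for a pause to determine attribution. The expedited-report sentence in VI.7 no longer applies, and the later sentences of VI.3 keep the event off the case report form. The opening sentence of VI.3 would record it.

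Case 2 is the severity gap. Case 5 is the mismatch of order, and it also shows section VI.3 disagreeing with itself about how long all events of grade 3 and upward are recorded.

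**Step 3. Extent.** The severity gap is all-or-none, because each trigger is a single event. For the mismatch of order, take a patient followed for the full 3 years and count 365 days a year: 3 × 365 = 1,095 days. Full capture covers 30 / 1,095 = 0.027, or about 3% of that time. The remaining 1,095 − 30 = 1,065 days fall under the related-only rule. This is a share of calendar time, not of risk, which may be concentrated near the infusion.

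**The case against.** The strongest reply is that the operative words are the serious unexpected events and the grade is only a parenthesis. On that view no investigator would read the rule as excluding an unexpected death. This is probably right about intent, and the wording looks like a drafting slip rather than a decision to carry on after a death. It does not cure the text, because the same protocol writes floors elsewhere and handles death separately without a pause.

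Other safeguards also exist. The IRB may terminate the study, deaths must be forwarded to it, the principal investigator reviews protocol-related results, and patients are examined at follow-up visits. These narrow the gap. None suspends enrolment automatically, and section VI.3 lets serious events attributed to the underlying disease or the first transplant reach the IRB only with the annual report. The 30-day limit also has a stated rationale, since these patients are often in hospital for earlier complications.

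A reader might infer four stronger things that the documents do not support:

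- *That no fatal event can suspend the trial.* The GVHD trigger covers a death with documented GVHD of grade II or above.
- *That the point rests on death being grade 5.* The documents do not define that grade. They support only that grade 4 is given without a floor and that death is not named.
- *That the suspension rule's window contradicts section VI.7.* The suspension rule has no window, and the 30 days in VI.7 govern reporting, not suspension.
- *That the rule cannot fire after day 30 unless an event is already judged related.* The event triggers the rule, not a form entry, and staff may learn of late events in other ways. What is established is that capture and suspension are not aligned.

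**Conclusion.** The point holds in this limited form and should be corrected. As printed, the suspension trigger and its counterpart for expedited reporting name grade 4 without a floor and omit death. One unexpected death not involving GVHD of grade II or above therefore does not, on the literal wording, suspend enrolment. Separately, the suspension rule has no stated window and presupposes that attribution is still open, while from day 31 the case report forms take only events for which attribution has been settled as related. The two recording statements in section VI.3 also need reconciling.

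The conclusion assumes that the text is followed as written and that no unseen operating procedure adds a pause for deaths. It does not assume that the sponsor meant to exclude deaths. No error rate or sample size is affected. The consequence is for safety oversight, and it matters more because the principal investigator monitors the trial alone.

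**What to change.** Amend the Stopping Rules and section VI.7 so that both triggers are written as a floor, grade 4 and upward, expressly including death from any unexpected event. State in the Stopping Rules the window during which the suspension rule applies; the sponsor and the IRB should choose it. Then reconcile section VI.3 with both, so that within that window every qualifying event is recorded before relatedness is decided, with attribution settled during the pause as the Stopping Rules already intend. The same edit should settle whether events of grade 3 and upward are recorded throughout the study or in full only to day 30.

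The cost is a short protocol amendment and, from time to time, a brief enrolment pause for a death later attributed to the underlying disease. If the chosen window ends at day 30, little capture is added. If it runs longer, the recording rule in section VI.3 must be widened for these events, with added work in a population that is often in hospital. How much depends on the window chosen.

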The purpose of this study is to investigate the usefulness of infusing purified CD34+ cells of donor origin in order to augment graft function in response to declining chimerism after initially performing an allogeneic hematopoietic stem cell transplant (HSCT) for children with primary immunodeficiency diseases. This protocol will be utilized for patients with waning mixed donor chimerism that is inadequate for correction of clinical condition or disease for which stem cell transplant was performed, or for augmentation of immune function. An infusion of selected CD34+ stem cells will be given without any preparative regimen. As the children eligible for this protocol have reduced immune function and pre-existing donor chimerism, we hypothesize that stem cells will be able to engraft and the infusion will augment graft function. This therapy serves as an alternative to a second stem cell transplant that is known to be associated with significant morbidity and mortality. CD34+ stem cells will be collected from the donor used for initial stem cell transplant. Cells will be T-cell depleted (TCD) by performing a CD34 selection using the CliniMACS device (Miltenyi Biotec) in order to prevent development of new or exacerbation of existing graft versus host disease (GVHD), as avoidance of GVHD in nonmalignant diseases is desirable. There is sufficient data showing that mixed donor chimerism is adequate for reverting disease phenotype in certain primary immunodeficiencies. Observations from Europe and CCHMC show that donor chimerism might be boosted by CD34+ stem cell infusion alone without any specific preparative regimen. This therapy is likely to be associated with low toxicity due to the absence of a preparative regimen and lack of exposure to fresh donor cells capable of initiating GVHD, and offers potential significant benefit.

I. PURPOSE OF STUDY

Hypothesis

Mixed or full donor chimerism that is adequate for disease control will be achieved with selected CD34+ stem cell infusion without preparative regimen with minimal or no therapy related toxicity or GVHD.

Objectives

- 1. Assess the toxicity of infusion of donor stem cells in augmentation of graft function in previously transplanted children with immune deficiencies, and bone marrow failures.
- Assess the efficacy of infusion of donor stem cells in augmentation of graft function in previously transplanted children with immune deficiencies, and bone marrow failures.

Endpoints

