The primary endpoint of the study is augmentation of graft function. Graft function will be measured in two ways. Firstly the percentage of donor chimerism, and secondly measured improvement in immune function; improvement in numbers of circulating white blood cells and/or platelets, and/or clearance of opportunistic viral infections.

 Improvement in immune function studies compared to baseline levels can be documented at 3, 6, and 12 months. Immune function studies will include quantitation of T and B cells and functional studies (mitogens and immunoglobulin levels). In the case of Wiskott-Aldrich syndrome, improvement of platelet count to >20,000/L on 2 separate occasions at least three months apart will be considered successful graft augmentation. Children requiring graft augmentation for a specific limited immune defect, e.g. inability to clear papilloma virus will also be assessed by clinical response of the infection; resolution or >50% improvement in infection will be considered successful graft augmentation.

The secondary endpoint is to determine the frequency and characteristics of potential infusion-related toxicity. Experience at our center, using CD34+ selected cells has shown infusion-related toxicity has occurred at an incidence of < 10% (zero toxicity in 9 patients participating in CCHMC IRB study # 2008-0777). While there is little expectation of infusion-related toxicity, the incidence of infusion-related reactions will be recorded and evaluated.

II. SIGNIFICANCE OF STUDY IN RELATION TO HUMAN HEALTH

Primary or congenital immunodeficiency diseases result from inborn genetic defects of the immune system frequently manifesting itself as recurrent and chronic infections and

commonly lead to lethal complications. Currently, more than 100 immunodeficiency diseases have been identified and classified according to the area of immune system that is compromised. Most of these have been molecularly defined and are due to single gene defects.

Allogeneic hematopoietic stem cell transplantation is the only curative approach to date for most of the lethal immunodeficiency diseases including severe combined immunodeficiencies (SCID), T-cell immunodeficiencies, Wiskott-Aldrich syndrome, Chediak-Higashi syndrome and others, where it restores immune function and decreases risk of long term complications such as malignant transformation.

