Infusional Toxicity: Infusion of stem cells could result in infusion reaction presenting as shortness of breath, fever, or anaphylaxis. To reduce the risk of infusion reaction, CD34+ stem cells will be highly T-cell depleted. While we have the expectation of a low occurrence of this toxicity, we will monitor for the frequency and characteristics of infusion related toxicities.

Statistical Analysis

We expect the frequency of adverse events in this study to be low (likely less than 5% events). We will therefore use all 45 patients to determine the frequency of adverse events as our ability to correctly define the frequency of events in any one stratum of 10 cases is low.

Descriptive statistics will be compiled on responding and non-responding cases, including patient and graft characteristics that might influence response. It is recognized that this portion of the analysis is exploratory due to the small sample size, but these data will be used to inform the design of future studies.

Stopping Rules

The primary endpoint of this study is qualitative graft augmentation. Five patients will be enrolled into each stratum for evaluation of graft augmentation. If none of the five patients per stratum show any graft augmentation, accrual to that particular stratum will be closed due to lack of efficacy. Patients will continue to be enrolled into other strata until criteria for five patients per stratum are fulfilled. If one out of five patients per stratum will meet listed criteria for graft augmentation, an additional five patients may be enrolled to that stratum.

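### The grade 3+ CRF threshold is not reconciled with an infusion-reaction endpoint that has no grade limit, and GVHD, named in the hypothesis, is not an endpoint

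*Combined protocol and SAP*

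**What the plan says.** **Infusion reactions.** Section I (Endpoints) makes infusion-related toxicity the secondary endpoint and promises that "the incidence of infusion-related reactions will be recorded and evaluated". Section 7 (Secondary Endpoints) repeats the aim: "we will monitor for the frequency and characteristics of infusion related toxicities". Neither place sets a grade limit. For the analysis, Section 7 (Statistical Analysis) says "We will therefore use all 45 patients to determine the frequency of adverse events".

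**What goes on the CRF.** Section VI.3 says "All grade 3 or greater adverse events occurring during this study will be recorded on the case report forms", graded by CTCAE v3.0. Later in VI.3, adverse events are captured for 30 days after infusion, with a reference back to that description. After day 30 only related events go on the CRF, and no grade is given. Section VI.7 repeats the related-only rule.

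**Other routes for reactions.** Section VI.2 says "Patients will be monitored according to CCHMC guidelines during stem cell infusion for any infusion reactions". Section 7 (Stopping Rules) says "Any fever occurring within twelve hours of the stem cell infusion requiring hospital admission will be considered an expected serious adverse event", to be reported promptly to the IRB.

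**GVHD.** The hypothesis expects disease control "with minimal or no therapy related toxicity or GVHD". The opening summary gives prevention of new or worsening GVHD as the reason for T-cell depletion. Documented GVHD of grade II or higher suspends the study (Stopping Rules). No primary or secondary endpoint mentions GVHD. Only uncontrolled GVHD is an exclusion, and the listed pre-infusion tests do not name GVHD status.

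**The concern.** An endpoint can count only what the data collection captures. The reactions the protocol expects (fever, chills, rash, shortness of breath) can be below grade 3. If the CRF is the source for the endpoint and its threshold is applied as written, the analysis yields a rate of grade 3+ reactions that readers could take for the rate of all reactions.

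GVHD raises a related problem. The hypothesis makes a claim about it, but the plan produces no GVHD incidence to test that claim. After day 30, recording depends on attribution. Attribution is difficult here because the same donor supplied both the first graft and the boost, and the principal investigator decides it without a DSMB or medical monitor.

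What is at stake is the safety half of the hypothesis: a near-empty table could be read as support for it when part of the relevant experience was never eligible to be counted.

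**Working it through.** The plan states no interval or precision target for the safety endpoint, so there is no figure to reproduce. The check is a comparison of the text, followed by illustrative arithmetic.

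**1. Infusion reactions, days 0 to 30.**
- Endpoint (Section I; Section 7): reactions with no grade limit.
- CRF (VI.3): grade 3 or greater, carried into the 30-day window by the back-reference.
- Exemption for infusion reactions: none in the available text.
- The promise in Section I to record incidence names no form, grading scale or time window.
- Bedside monitoring and the fever rule may bring a reaction to notice, but neither yields a rate covering all grades.

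**2. GVHD, by route.**
- Grade II or higher: must be noticed for the suspension rule to work. That is a safety action, not an incidence analysis, and its grading is not linked to the CTCAE grade 3 threshold of the CRF.
- Grade I at any time, or below CTCAE grade 3 in the first 30 days: no stated route into a table.
- After day 30, judged related: goes on the CRF. Read literally, this covers any grade, though it can also be read as a subset of grade 3+.
- After day 30, judged unrelated and serious: VI.3 sends events attributed to the first transplant to the annual IRB report.
- After day 30, judged unrelated and not serious: no stated route.

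**3. Length of GVHD follow-up.** The Schedule table under Procedures runs clinical assessment yearly to 3 years. Required Observations, to which the table refers for details, lists it only to twelve months.

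**4. What a count of zero would mean.** Inputs: n = 45 (Section 7) and exact Clopper-Pearson two-sided 95% limits. For zero events the upper limit is 1 − 0.025^(1/n). Otherwise the limits solve P(X ≥ x | p) = 0.025 and P(X ≤ x | p) = 0.025.
- 0/45: upper limit 1 − 0.025^(1/45) = 7.9%.
- 1/45 = 2.2%: 0.06% to 11.8%.
- 2/45 = 4.4%: 0.54% to 15.15%.

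Each uncounted patient moves the estimate by 1/45 = 2.2 percentage points. The one and two patients are illustrations, not estimates. The earlier experience, "zero toxicity in 9 patients participating in CCHMC IRB study # 2008-0777", does not settle the matter: its upper limit is 1 − 0.025^(1/9) = 33.6%, and its grade threshold is not stated.

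**5. How easily a zero could arise (assumption, with range).** Let p be the rate of reactions of any grade and s the share that is grade 3+. Then P(no CRF entry among 45) = (1 − ps)^45. Take p = 5%, the ceiling that Section 7 expects for adverse events, applied here to reactions by assumption. The expected number of patients with a reaction is 45 × 0.05 = 2.25. The values of s are assumed.

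| s | (1 − 0.05s)^45 |
|---|---|
| 10% | 80% |
| 25% | 57% |
| 50% | 32% |
| 100% (every grade recorded) | 9.9% |

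The documents give no value for s, so this shows the mechanism and does not measure the under-count.

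**The case against.** The strongest reply is that VI.3 sets a minimum. It says all grade 3+ events are recorded, not that only those are, and the protocol uses the word only where it means to restrict. Section I adds a specific duty to record reaction incidence, and VI.2 requires monitoring for any reaction. A general minimum and a specific duty can coexist. This stands to the extent that the passages do not flatly contradict each other. A reader might infer that the plan means to ignore low-grade reactions, and the documents do not support that. What remains is that staff could comply with VI.3, omit them, and leave the endpoint incomplete.

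Other stronger readings also fail:
- *Grade 3+ is the only CRF rule.* It is the only grade threshold; the related-only rule after day 30 states no grade.
- *GVHD attributed to the first transplant goes wholly unreported.* Serious events of that kind are reported annually to the IRB, and grade II or higher must be noticed for the suspension rule.
- *There is no GVHD baseline.* Excluding uncontrolled GVHD implies some judgement at entry, and disease status and organ function are evaluated before infusion. What is missing is a stated requirement to record GVHD status.
- *One omitted reaction decides whether toxicity stays below 10%.* That figure in Section I describes earlier experience. No rule compares a confidence limit with it.

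It is also fair to say that a formal GVHD endpoint is partly a design choice in a small descriptive study, and that recorded GVHD could fall under the general toxicity objective. But the hypothesis names GVHD, so a tabulated incidence is needed to check it.

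**Conclusion.** The point holds as an unreconciled definition, not as proof that events will be lost. The only grade threshold stated for the CRF is grade 3+, while the secondary endpoint has no grade limit. If the CRF rule is followed, grade 1-2 reactions may be left out. GVHD is hypothesised and acts as a suspension trigger but is not an endpoint, and the gap in its counting is confined to the lower-grade, early and non-serious unrelated cases listed above.

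The size of any under-count cannot be computed, and no GVHD magnitude can be derived. A result of 0/45 would bound the rate at 7.9%, for the recorded grades only.

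This rests on two conditions: that the CRF is the data source for the endpoint, and that nothing in the parts of the protocol missing from the available text, or in the CRFs themselves (not among the documents), supplies the missing rule. The change should be made; confidence is medium.

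**What to change.** 1. In Section VI.3, exempt infusion reactions from the grade 3+ threshold. Record every grade (CTCAE v3.0), type and time within a stated window, for example to the Day 7 visit. Report the number and percentage of infused patients with an exact 95% confidence interval.
2. List GVHD as a secondary safety outcome. Record its status before infusion. At the existing clinical assessments, record new or worsened acute or chronic GVHD with grade and onset date, regardless of attribution. Report incidence with an exact 95% confidence interval.
3. Reconcile the Schedule table with Required Observations so that the GVHD follow-up period is defined.

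The suspension rule and the grade 3+ rule for other events stay unchanged.

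The cost is some protocol wording and a few CRF lines. Infusion monitoring and visits to twelve months are already planned; whether later GVHD assessment adds work depends on how item 3 is resolved. The downside is more low-grade entries and a less favourable-looking safety table.
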